We will use a mixed models approach to examine **secondary outcome measures (Specific Aim 2)** for a statistically significant difference in; drinks per week, and heavy drinking days per week, the outcomes used in the pilot study. The model will include fixed effects for medication group, week, and the interaction between medication and week, also controlling for pre-treatment drinking behavior data, and using a random effect for intercept. We will incorporate a grace period corresponding to the time it takes to titrate the medication to target dose into the models, and we will focus the primary analysis on the 8 weeks of treatment at the target dose. Aggregate outcome measures such as the percentage of heavy drinking days, which can be examined using several different methods, will be considered. A statistically significant difference on any of the secondary measures of both heavy drinking and drinking, with clinically significant effect sizes, will be considered a relative success for the medication. Additional secondary outcome measures will include changes in GGT level, measures of alcohol urge or craving to use (AUQ), measures of depression and anxiety, measures of physical health and quality of life (Q-LES-Q, the and the RAND-36) and level of alcohol-related problems (as measured on the SIP). These can also be performed with the mixed models approach. Statistical models evaluating time to relapse, drinking trajectories, percentage of abstinent days, drinks per drinking day, and total abstinence rates will be considered. **We will use the Bonferroni correction for the secondary outcomes and additional comparisons to guard against chance findings.**

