All secondary outcome analyses will be by intention to treat, a conservative approach that is aimed at avoiding an overestimation of the treatment effect and will include all subjects that take any medication and provide drinking data for at least one week. The use of multilevel repeated measure statistical models may increase the study power and potential to detect a treatment effect. This type of repeated-measures analysis 1) provides missing-data imputation procedures that are both conservative and logical; 2) allows for the measurement of the exact time that a given patient is measured at baseline and follow-up points, which need not be the same among patients; 3) plots and analyzes linear and non-linear time-course functions both overall and for subgroups of patients based on each patient's best estimate linear and non-linear regression line plots. We will use all available data on individuals and thus dropouts provide data until the point of dropout. The best-fitting variance-covariance structure between the repeated measures will be selected based on Schwartz-Bayesian Information Criterion (BIC). We will compare dropout patterns between groups and if there are concerns of informative dropout and/or informative intermittent missing data, we will use pattern mixture models (Hedeker and Gibbons, 1997) to perform sensitivity analyses to our main analyses. Adherence to the medication will be evaluated and factored into the analysis. We will evaluate and compare both medication conditions (placebo, ZNS) for percentage of prescribed pills taken. We do not expect a difference, but if one is found, we can then perform additional analysis on the main outcome variables to estimate treatment effects adjusted for percent pills taken. The number of MM sessions attended will be recorded and analyzed similar to the medication adherence.

The three-month follow up data will be gathered using a retrospective TLFB at the follow-up time point, and will be analyzed using logistic regression for PSNHDD, and either linear mixed models or Hierarchical Linear Modeling (HLM) for other outcomes. We will examine that drinking data between the end of treatment and the three-month time point and use the same outcomes as the main analysis. We will be able to examine for persistent effects of ZNS on drinking behavior and related outcomes. These analyses will include pre-treatment and within-treatment drinking data as covariates to evaluate the post-treatment effects of ZNS.

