6.I.6. Sample Size And Power Estimate (Specific Aims 1-3):

For the primary outcome PSNHDD: Based on the trend in the pilot study favoring ZNS with 12 subjects in the ZNS group without relapse to heavy drinking, and only 7 in the placebo group, we estimated the power with the previously planned sample size. Based on these proportions, we should be well powered (>89%) to detect a difference in PSNHDD with 80 in each group. Since dropouts will be counted as relapsed to heavy drinking, we will still be powered at that level, regardless of the number of dropouts. Even in the event that we don't recruit as many subjects as expected (e.g., N=64 in each group, approximately) we estimate the estimated power will be about 76% to detect a difference between the medication and placebo.

For secondary outcomes: Based on the effect sizes from our pilot study of ZNS (showing a small effect size on heavy drinking and a moderate effect size on total drinking), we estimated that a study with **N=160** (subjects) would be well powered (>.98) to detect a significant difference on the secondary outcomes heavy drinking days per week, and total drinks per week. In our pilot study we ran a linear mixed models and found a decrease in drinking of 1.4 drinks per week for the controls versus 2.2 drinks per week for ZNS. The variance in the decrease in drinking (slope) was approximately 0.9. Assuming similar results, a Monte Carlo simulation in Mplus showed that with a sample of 160 subjects evenly split between groups and measured weekly over 12 weeks there is power of 0.98 to detect a significant difference in slopes between groups. Also, in our pilot study we found a decrease in heavy drinking days per week of 0.2 for the controls versus 0.3 for ZNS. The variance in the decrease in drinking (slope) was about 0.1. Assuming similar results, a Monte Carlo simulation in Mplus showed that with a sample of 160 subjects evenly split between groups and measured weekly over 12 weeks there is power of 0.99 to detect a significant difference in slopes between groups. **Even if dropouts reached 40%, we will be well powered (>.80) for detecting differences on secondary outcomes.**

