6.I.7. Pharmacogenetic Data Analyses and Power Estimate (Exploratory Specific Aim 4): We will explore the interaction of the DBH SNP and ZNS described in section B.3.e, in terms of treatment response using mixed models or logistic regression where appropriate. With an N=160 we should be well powered to detect an effect of the DBH SNP, based on our previous study, from which we calculated an OR of approximately 12.6 for those on naltrexone with the advantageous allele (Cohen's d = 1.4). Given the large effect size observed, albeit from one small study, we should be well powered (> .99) to find a significant pharmacogenetic interaction if it exists on PSNHDD or secondary outcomes. Using the more conservative effect size from the Wald chi square logistic regression model for the DBH genotype-naltrexone interaction, (Cohen's d = .5), we should be well powered (>.99) to find a similar interaction for ZNS. Given the exploratory nature of the pharmacogenetic analyses, they will not be corrected for multiple comparisons. Estimates of effect sizes will be used for replication of the findings in appropriately powered future studies.

6.J. Timeline For Recruitment And Other Study Objectives: As shown in Table 4, recruitment will take place over 45 months, requiring enrollment of approximately 40 total patients per year (or approximately 2 patients/month at each site).

Table 4: Timeline of Performance Goals

Activity	Year 1	Year 2	Year 3	Year 4	Year 5
Staff training & study preparation					
Patient enrollment					
Endpoint assessments					
3-month follow-ups					
Data entry & cleaning					
Data analysis					
Report writing					

6.K. Plan For Managing And Integrating The Two Clinical Sites: This project will take place at two sites: the West Haven VAMC (VA Connecticut Health System) and the Bedford VAMC (both of which are in VISN1). The principal investigator ([name].) and Bedford site investigator ([name].) have agreed to engage in this collaborative effort, each bringing expertise in alcohol research that will be synergistic. Working together, the partnering sites will operate via a steering committee that will ensure the integrity of the research plan with an emphasis on safety, adherence to the protocol, and the integrity of the data and its analysis. The researchers will build upon the existing relationship between the investigative groups that has resulted in a successful collaboration for more than ten years.

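### The power of 0.99 for heavy drinking days per week does not follow from the inputs printed with it, which give at most about 0.51

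*Combined protocol and SAP*

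**What the plan says.** Section 6.I.6 sets out the secondary-outcome power. For heavy drinking days per week it states that "in our pilot study we found a decrease in heavy drinking days per week of 0.2 for the controls versus 0.3 for ZNS", followed by "The variance in the decrease in drinking (slope) was about 0.1". With 160 subjects split evenly, the simulation is reported as "measured weekly over 12 weeks there is power of 0.99 to detect a significant difference in slopes between groups". The paragraph opens with a claim of power above .98 for both secondary drinking outcomes and closes with "Even if dropouts reached 40%, we will be well powered (>.80) for detecting differences on secondary outcomes". It describes the pilot effect as small for heavy drinking and moderate for total drinking.

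The analysis being powered is in section 6.I.2: a mixed model with medication, week and their interaction, and a random effect for the intercept. There, "we will focus the primary analysis on the 8 weeks of treatment at the target dose", and "We will use the Bonferroni correction for the secondary outcomes and additional comparisons to guard against chance findings". On missing data, "We will use all available data on individuals and thus dropouts provide data until the point of dropout".

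Section 6.I.7 claims power above .99 for the DBH interaction at d = 1.4, and then again at a smaller effect: "Cohen's d = .5), we should be well powered (>.99) to find a similar interaction for ZNS".

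**The concern.** A slope difference of 0.1 against a slope variance of 0.1 is a standardised difference of about 0.3, which 80 per arm detects only about half the time. The section also gives the effect it calls small a higher power (0.99) than the one it calls moderate (0.98).

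Heavy drinking days per week appears in the hypothesis under Aim 1 and as an outcome under Aim 2, and section 6.I.2 counts significant secondary drinking results towards judging the drug a relative success. With power stated as 0.99, a null result would read as near-decisive evidence against an effect of the pilot size. On the printed inputs, a null would be about as likely as not even if that effect were real. The DBH analysis is exploratory, so the harm there is limited to an unsupported power statement.

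**Working it through.** **Inputs (section 6.I.6).** Heavy drinking days: slopes 0.2 and 0.3, difference 0.1, slope variance 0.1. Drinks per week: slopes 1.4 and 2.2, difference 0.8, slope variance 0.9. 80 per arm, 12 weekly measures. Alpha is not stated for these figures; two-sided 0.05 is assumed.

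**Formula.** With complete data, a subject's estimated slope has variance (slope variance) + (residual variance)/Sxx, where Sxx = 143 for 12 equally spaced weeks. Setting the residual variance to zero gives a ceiling on power:

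SE = √(2 × slope variance / n per arm); power ≈ Φ(difference/SE − 1.96).

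**Check on drinks per week.** SE = √(2 × 0.9/80) = 0.15 and 0.8/0.15 = 5.33, so the ceiling is Φ(3.37) = 0.9996. The stated 0.98 follows with a residual SD of about 10 drinks per week. With 48 per arm (40% lost), SE = 0.194 and the ceiling is 0.985 (0.983 by noncentral t). The method therefore accommodates both the 0.98 and the >.80 for this outcome.

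**Heavy drinking days, no dropout.** SE = √(2 × 0.1/80) = 0.05 and 0.1/0.05 = 2.0, so power = Φ(0.04) = 0.516, or 0.511 by noncentral t (d = 0.1/√0.1 = 0.316). Residual variance only lowers this: 0.498 at 0.5 and 0.461 at 2 (noncentral t). Power of 0.99 at 80 per arm needs d of about 0.68, roughly double the printed value. At the printed d it needs about 368 per arm.

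**Heavy drinking days, 40% dropout.**
- Completers only, 48 per arm: SE = √(2 × 0.1/48) = 0.0645, ratio 1.55, power 0.341 (0.335 by noncentral t).
- With dropouts' partial data, as section 6.I.2 plans: no dropout can contribute more than a full slope, so the ceiling stays at about 0.52. For illustration, dropout times uniform over weeks 1–11 and residual variance 2 to 0.5 give about 0.39–0.45. Those values are assumptions, not in the documents.

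**What could reconcile the figures.** Slopes and variance are printed to one decimal, so the true difference could lie anywhere from near 0 to near 0.2, and the variance from 0.05 to 0.15. Ceilings at 80 per arm (noncentral t):

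| Difference | Variance | Ceiling |
|---|---|---|
| 0.05 | 0.10 | 0.17 |
| 0.10 | 0.10 | 0.51 |
| 0.10 | 0.05 | 0.80 |
| 0.15 | 0.10 | 0.85 |
| 0.15 | 0.05 | 0.988 |
| 0.20 | 0.10 | 0.978 |
| 0.20 | 0.08 | 0.994 |
| 0.20 | 0.05 | 0.9999 |

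Alternatively, if 0.1 is a standard deviation, d = 1.0, the ceiling exceeds 0.999, and 0.99 follows with a residual variance of about 1.7.

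**DBH at d = .5, N = 160 (section 6.I.7).**
- Equal two-group contrast, one outcome per subject: 0.5 × √(80/2) = 3.16, power Φ(1.20) = 0.885 (0.882 by noncentral t).
- If d is a difference of treatment differences between genotypes: SE in SD units = √(4/n_CC + 4/n_T). With 80/80 this is 0.316, ratio 1.58, power 0.35. With 128/32 it is 0.395, ratio 1.26, power 0.24. The CC share of 50% to 80% is assumed.
- At d = 1.4, >.99 is reproduced for the equal two-group contrast.

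**The case against.** **Rounding.** The printed figures are too coarse to fix the power. Favourable corners reach 0.99 or more, and at 48 per arm a difference of 0.2 with variance 0.08 still gives a ceiling of 0.93. This stands, and it is why the point is a mismatch with the printed inputs and not a demonstrated simulation error. But 0.99 needs both inputs to move favourably and close to their limits; moving either one alone does not reach it. Unfavourable corners fall below 0.17.

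**The planned model names only a random intercept.** The 0.51 ceiling applies to a test that allows slopes to vary between subjects. Simulating the printed inputs and analysing them with a random intercept only gives rejection in roughly 0.85–0.92 of runs at 80 per arm and 0.72–0.84 at 48 per arm (residual variance 2 to 0.1). This also stands as a fact about the wording of section 6.I.2. It does not rescue the claim: the same analysis rejects in roughly 0.4–0.55 of runs when there is no effect, and it still falls short of 0.99.

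**DBH.** Section 6.I.7 allows mixed models on secondary outcomes, and d is undefined. A two-group contrast on repeated measures, with d scaled to a single week and an assumed correlation of 0.5, gives about 0.99. So 0.88 is not an upper limit under every reading. The section, however, takes d from a logistic Wald statistic and does not describe that design. As a true interaction, the same repeated-measures setting gives only 0.56–0.57.

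**Importance.** The outcome is secondary in the power section and DBH is exploratory. That is accepted.

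**Conclusion.** The concern holds as an inconsistency between printed inputs and stated power. At face value, heavy drinking days per week has power of at most about 0.51 against 0.99 stated. At 40% dropout it has about 0.34 on completers, and no more than about 0.52 with partial data, against >.80 stated. This assumes a two-sided 0.05 test that allows for between-subject slope variance. The planned Bonferroni correction would lower it further: halving alpha to .025, for illustration, gives about 0.40.

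A reader might infer that the true power is 0.51, or that the simulation was wrong. The documents support neither: rounding, an SD printed as a variance, and a simulation error all remain possible. A reader might also infer that the dropout claim fails for every secondary outcome, or that the trial is too small. The drinks-per-week figures are attainable, and nothing here bears on N = 160 or on the PSNHDD power.

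For DBH, >.99 at d = .5 is not reproduced on the readings the section describes (about 0.88, or 0.24–0.35 as a difference of differences). The conclusion is that the figure is undefined as written, not that a firm lower value is established.

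**What to change.** - Check the pilot output and the simulation inputs for heavy drinking days. Print the slopes and slope variance to enough decimals to reproduce the result, and say whether 0.1 is a variance or an SD.
- Correct either the inputs or the 0.99, and with it the opening >.98 and the 40%-dropout >.80 as they apply to this outcome.
- Rerun the power for the analysis in section 6.I.2: 8 weeks at target dose instead of 12, the Bonferroni alpha with the number of tests stated, and between-subject slope variance modelled. State the residual variance and how dropouts' partial data enter.
- In section 6.I.7, define d, give the assumed genotype split, and restate the power at d = .5.

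The cost is a look at existing output, one simulation rerun and a few sentences of text. The restated power may be less favourable. N, visits and data collection do not change.

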We will use the percentage of subjects with no heavy drinking days (**PSNHDD**) as the primary outcome variable. This outcome is the FDA recommended endpoint for pivotal trials, and is described in Falk et al., (2010). The PSNHDD can be derived from each subject's TLFB data. An important initial consideration in considering effectiveness will be to identify baseline differences between groups that may have occurred despite randomization. **Successful outcomes during the treatment trial will be defined in terms of a statistically significant difference on the primary outcome measure: PSNHDD, compared during the 8 weeks of active treatment at the target dose, allowing for a 6 week grace period for the medication titration.** For all analyses, heavy drinking days will be defined as follows; for men > 5 drinks in a day and for women > 4 drinks in a day. Patients will be followed irrespective of whether they continue to receive medication treatment, so that analysis will include all data available for the 8-week treatment period. The analysis will be **intent-to-treat**, and dropouts will be considered as having relapsed to heavy drinking. We will use a logistic regression analysis with PSNHDD as a categorical dependent variable. Medication condition (placebo or ZNS) will be the main independent variable, and we will include the variables of early onset of alcoholism (EOA, binary), and the use of additional psychotropics (e.g., antidepressants, a binary variable) as covariates. The α will be set at .05 for the primary outcome variable. Between site differences will be explored.

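### The secondary-outcome power in 6.I.6 (0.98, 0.99, and >.80 at 40% dropout) is not shown to hold under the Bonferroni correction planned in 6.I.2

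*Combined protocol and SAP*

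**What the plan says.** Section 6.I.2 of the combined protocol and SAP uses mixed models to test the secondary outcomes "for a statistically significant difference in; drinks per week, and heavy drinking days per week, the outcomes used in the pilot study". It then lists more: "Additional secondary outcome measures will include changes in GGT level, measures of alcohol urge or craving to use (AUQ), measures of depression and anxiety", followed by Q-LES-Q, RAND-36 and SIP. Counting depression and anxiety separately, that makes nine named outcomes. Five others (such as time to relapse and drinks per drinking day) are only to be considered, which would make fourteen. On multiplicity it says "We will use the Bonferroni correction for the secondary outcomes and additional comparisons to guard against chance findings", with no family and no divisor. The only significance level in the plan is in the same section: "The α will be set at .05 for the primary outcome variable".

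Section 6.I.6 bases the secondary power on Mplus simulations from the pilot. For drinks per week the pilot "found a decrease in drinking of 1.4 drinks per week for the controls versus 2.2 drinks per week for ZNS", with slope variance about 0.9, and "with a sample of 160 subjects evenly split between groups and measured weekly over 12 weeks there is power of 0.98". For heavy drinking days per week the slopes are 0.2 and 0.3, the variance about 0.1 and the stated power 0.99. It closes with "Even if dropouts reached 40%, we will be well powered (>.80) for detecting differences on secondary outcomes". It does not mention alpha, sidedness, residual variance or the correction.

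**The concern.** Power is tied to the test that will be run. If the simulations used one .05 test per outcome, as the silence in 6.I.6 suggests, the printed figures describe a more lenient test than the corrected one in 6.I.2. The gap is small at full sample size, but it could remove the reassurance about 40% dropout. It matters because 6.I.2 lets a significant secondary difference on drinking count as a relative success for the drug. A reader who trusts the stated power would also take a null secondary result as stronger evidence of no effect than it may be.

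**Working it through.** **Inputs (6.I.6).** 80 per arm; drinks-per-week slope difference 2.2 − 1.4 = 0.8, variance 0.9, stated power 0.98; heavy-drinking-days slope difference 0.3 − 0.2 = 0.1, variance 0.1, stated power 0.99; 12 weekly measures. All results use the normal approximation, two-sided.

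**1. The plan's own figures.** Using slope variance alone, which gives an upper bound because residual variance is not reported:
- Drinks per week: SE = √(2 × 0.9/80) = 0.15; 0.8/0.15 = 5.33; power = Φ(5.33 − 1.96) = 0.9996. The stated 0.98 lies below this bound and is compatible with it. The match does not reveal the alpha: the same shortcut gives 0.995 at .05/9 and 0.992 at .05/14.
- Heavy drinking days: SE = √(2 × 0.1/80) = 0.05; 0.1/0.05 = 2; power = Φ(2 − 1.96) = 0.516. The stated 0.99 is not reproduced. It would need 2 × 0.1 × (1.960 + 2.326)²/0.1², about 368 per arm. Power is near 1 only if the 0.1 is a standard deviation rather than a variance.

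**2. Applying the correction to the stated 0.98.** Assume that "there is power of 0.98 to detect a significant difference in slopes between groups" refers to one two-sided .05 test. The noncentrality is then 1.960 + z(0.98) = 1.960 + 2.054 = 4.014. With k tests, power = Φ(4.014 − c), where c = z(1 − .025/k). If 40% are lost and contribute nothing, the noncentrality is 4.014 × √0.6 = 3.109.

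| k | c | N=160 | 40% lost, no data from dropouts |
|---|---|---|---|
| 1 | 1.960 | 0.98 | 0.875 |
| 2 | 2.241 | 0.962 | 0.807 |
| 3 | 2.394 | 0.947 | 0.763 |
| 5 | 2.576 | 0.925 | 0.703 |
| 9 | 2.773 | 0.893 | 0.632 |

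**3. Letting dropouts contribute.** Section 6.I.2 keeps each dropout's data up to the point of leaving, so the last column is a worst case. To relax it, back-solve the residual variance. The implied total variance is 40 × (0.8/4.014)² = 1.589. Subtracting 0.9 leaves 0.689, and multiplying by 143 (the sum of squared deviations of 12 weekly times) gives a residual SD of about 9.9 drinks per week. Spreading the 40% dropout evenly over weeks 2 to 11 then gives 0.889 (k=2), 0.858 (k=3), 0.813 (k=5) and 0.755 (k=9). A cruder version, treating the effective loss as 20%, gives 0.884 (k=3) and 0.793 (k=9).

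**4. Analysis window.** The simulation uses 12 weekly measures, but 6.I.2 focuses on 8 weeks at target dose. With the same back-solved residual variance and 42 in place of 143, the variance is 0.9 + 98.5/42 = 3.25, and power at N=160 without dropout is about 0.80 uncorrected, 0.715 at k=2 and 0.51 at k=9. This illustrates sensitivity and is not a replacement estimate.

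**The case against.** A reader might infer that the stated power is simply not delivered. The documents do not support that. The simulation alpha, the family size and the residual variance are all missing. If a corrected alpha was used, 0.98 stands for drinks per week. On the printed drinks-per-week inputs with slope variance alone, power with 48 per arm (40% lost) is 0.913 at nine tests and 0.888 at fourteen. Those are upper bounds, so they do not vindicate the claim, but they do rule out calling the shortfall certain.

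Three further points stand in part:
- The family of nine is a count of the outcomes named in 6.I.2, not a number the plan adopts. The closing sentence of 6.I.6 can be read as covering only the two drinking outcomes. For two tests, >.80 holds for drinks per week even with dropouts discarded (0.807).
- The 0.63 contradicts the planned use of partial data and should not be taken as the power at 40% dropout. Even so, at nine tests all three dropout assumptions tried stay below .80 (0.632, 0.755, 0.793).
- Specific Aim 1 calls drinks per week the primary measure. If that governed, the secondary correction would not reach it. Sections 6.I.2 and 6.I.6, however, both treat it as secondary.

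**Conclusion.** The point holds as an omission: the secondary power is not shown under the planned correction. Everything computed from 0.98 assumes one two-sided .05 test. On that assumption the full-sample loss for drinks per week is modest (0.98 to about 0.96 for two tests, 0.89 for nine). The 40% dropout claim depends on the family: it survives for two outcomes and fails for nine. Between those it depends on how dropout is modelled; five tests give 0.70 or 0.81. These dropout results keep the 12-week window of the simulation.

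The heavy-drinking-days figure is a separate and firmer problem. Its printed inputs give at most about 0.52 before any correction, and about 0.34 with 48 per arm, so neither 0.99 nor >.80 follows from them.

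**What to change.** In 6.I.2, name the Bonferroni family and its size k. One option is to limit it to the two simulated drinking outcomes and label the rest exploratory. In 6.I.6:
- state the alpha, sidedness and residual variance;
- rerun both simulations at .05/k over the 8-week analysis window, with dropouts' partial data kept;
- replace 0.98, 0.99 and >.80 with the results;
- check whether the 0.1 for heavy drinking days is a variance or a standard deviation, and correct that figure in the same rerun;
- limit the 40% dropout statement to the outcomes simulated.

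The 0.89 and 0.63 above are back-solved approximations and should not be printed as replacements. A rerun that changed only the alpha would leave the heavy-drinking-days inputs and the 12-week window uncorrected. The cost is one rerun and some rewording, with no change to sample size or conduct; the downside is a less favourable stated secondary power.
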